### Design:

A small randomized controlled trial design will be conducted online at two time points: 1) baseline/pre-test and 2) post-test (one week after pre-test). The study questionnaires will be programmed into an online data collection system and the intervention itself is also completed online.

Participants will be randomly assigned to one of two conditions: 1) intervention (youth will receive access to *DKIN: Teen* right away) or 2) wait-list control (youth will not have access to the intervention between pre-test and post-test assessments; after completing the post-test questionnaire, youth will be given the option to review *DKIN: Teen*).

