### Methods:

*Sample and Recruitment.* Youth between the ages of 12 and 17 will be recruited for the study. To be eligible to participate in the study, the following criteria must be met. Youth in the study must: 1) be between the ages of 12 and 17 years; 2) understand English because the resource and questionnaires are in English; 3) have access to a computer or tablet with internet access for the duration of the study as the intervention and questionnaires are web-based; 4) NOT currently be in or have previously participated in a clinical trial. This study will investigate if the intervention improves attitudes and decision-making of youth who have not yet participated in a clinical trial; thus, excluding those who have already had the experience of being in a clinical trial. Youth will be recruited from across the United States via flyers and a study website in addition to recruitment efforts via Peachjar (digital flyer service used by school districts) and pediatric health organizations and advocacy groups. Efforts will be made to ensure that the intervention and wait-list control groups have about equal amounts of boys and girls as well as healthy youth and youth with varying chronic diseases/disorders and represent diversity in race and ethnicity.

*Procedure.* Parents of interested adolescents will visit the study recruitment website to learn more about the study and respond to the study eligibility screening questions. Parents will be notified onscreen immediately if their child is eligible to participate in the study, and if so, will be given access to online permission and assent forms. They will be instructed to review the forms together so they can decide about participation. Interested participants who decide to complete the forms will be told that in an attempt to have a diverse sample, they may not be

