### *Measures.*

**Knowledge.** This measure has been created for the purposes of this study. Youth will respond to questions that assess their factual knowledge about clinical research (e.g., What is a clinical trial?). Questions are in multiple choice format (some questions have multiple correct answers), and the total score will be calculated.

**Attitudes and Beliefs (adapted from Madsen, Mirza, Holm, Hilsted, & Riis, 2002).** Youth will be asked to respond to questions that assess their positive attitudes about clinical trials (e.g., How do you feel about kids participating in clinical trials?; 1=Not good at all; 2=Not very good; 3=Not sure; 4=Good; 5=Very good) and questions that assess their beliefs about positive aspects of pediatric clinical research (e.g., I believe that clinical trials can help kids; 1=Strongly Disagree; 2=Disagree; 3=Unsure; 4=Agree; 5=Strongly Agree).

**Self-Efficacy (adapted from Bandura, 2006).** Youth will be asked to respond to questions related to their self-efficacy for making decisions related to participation in clinical trials for two areas: 1) gathering information about clinical trials (e.g., Ask my parents questions for more information about clinical trials?); 2) communicating about clinical trials (e.g., Tell the researcher that I don't want to participate in the clinical trial, even if they really want me to do it). Youth will rate each question on a 5-point Likert scale (1 = I cannot do it at all; 5 = I know I can do it). Youth will be asked to respond to additional items to measure youths' confidence for participating clinical trials (e.g., I know what rights I have in a clinical trial. I know whom to ask if I need more information about a clinical trial.; 1=Strongly Disagree; 2=Disagree; 3=Unsure; 4=Agree; 5=Strongly Agree).

**Procedural fears (adapted from Kowalsky, France, France, Whitehouse, & Himawan, 2014).** Youth will be asked to respond to questions related to their perceptions of fear or anxiety about different types of medical procedures, including getting a needle in the arm, injection in the leg, getting a scan, and taking new medicine, on a 5-point Likert scale (1 = Not at all afraid or anxious, 2 = Somewhat afraid or anxious, 3 = Moderately afraid or anxious, 4 = Very afraid or anxious, 5 = Extremely afraid or anxious).

**Fidelity of Implementation.** iRT's LMS will record the amount of time that users spend on the website components and the specific components that were reviewed.

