**Consumer Satisfaction Questionnaire (CSQ)** will assess satisfaction for each of the three components of the website in terms of: (1) content (e.g., The information in the Spotlights was interesting to me.); (2) format (e.g., I liked that there were games and activities I could play in the Investigations.); (3) usability (e.g., I could figure out how to make the Comics work.). Overall quality will also be assessed (e.g., I would recommend this resource to a friend that was considering participating in research.). Participants will rate each item on a 5-point Likert scale (1 = Strongly Disagree, 2 = Disagree, 3 = Undecided, 4 = Agree, and 5 = Strongly Agree).

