## Statistical Analysis Plan

**Preliminary Analyses.** Chi-squared analyses will be used to examine if the randomization process produced equivalent groups between the wait-list control and intervention groups with respect to gender, race, ethnicity, health status, and SES. A t-test will be used to examine if the randomization process produced equivalent groups between the wait-list control and intervention groups with respect to age. If any of these demographical variables are found to differ significantly between the two groups, they will be included as covariates in the main analyses. Finally, the outcome variables will be examined to see if the values are normally distributed.

*Main Analyses.* Intent-to-treat (ITT) analyses will focus on examining the feasibility of *DKIN: Teen* for making positive changes in youth outcomes related to participation in clinical trials. A series of single factor, condition (intervention, wait-list control) random effects ANOVA models will be used to examine if using *DKIN: Teen* impacts the posttest 1) knowledge, 2) attitudes, 3) beliefs, 4) self-efficacy, 5) fears related to participation as well as likelihood to participate and 6) likelihood that fears would prevent participation. Pretest scores for each outcome will be included as predictor variables; therefore, outcome variable means will be adjusted posttest scores. Because this study is not powered to find significant differences (i.e., p-values) between groups, small or larger effect sizes (Cohen's d) will be emphasized during interpretation as evidence of feasibility.

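### The SAP treats a small Cohen's d as evidence of feasibility, but plans no confidence interval for d and names no SD for it

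*Combined protocol and SAP*

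**What the plan says.** The closing sentence of Main Analyses in the SAP gives the only rule for interpreting the outcome comparisons. It begins "Because this study is not powered to find significant differences (i.e., p-values) between groups, small or larger effect sizes" and concludes that these effect sizes, expressed as Cohen's d, "will be emphasized during interpretation as evidence of feasibility". The preceding sentence fixes the numerator of d: "Pretest scores for each outcome will be included as predictor variables; therefore, outcome variable means will be adjusted posttest scores".

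The document mentions no confidence interval, standard error or other statement of precision for d. It gives no numeric value for *small*. It does not say whether the adjusted difference is divided by a pretest, posttest, control-group or model residual SD. No sample size appears either; the Design section says only "A small randomized controlled trial design will be conducted online at two time points".

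Other information on feasibility is planned under Measures. For usage, the website's "LMS will record the amount of time that users spend on the website components". For satisfaction, a questionnaire covers content, format and usability, and "Overall quality will also be assessed".

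**The concern.** Low power is a good reason not to lean on p-values. It is not a reason to give weight to a small d, because the imprecision that makes the test weak makes d equally uncertain. Without an interval, the reader cannot tell a small effect from chance variation.

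The word feasibility does not remove the difficulty. Main Analyses ties feasibility to bringing about favourable change in the youth outcomes, so d is being used to support a claim about effect. If the plan is followed as written, a small estimate compatible with no effect can be reported as support.

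The unnamed SD is a secondary matter. After pretest adjustment the residual SD is smaller than the raw SD, so the same mean difference gives a larger d. On the residual scale d also depends on each outcome's own pretest-posttest correlation, which makes values harder to compare across outcomes.

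**Working it through.** The plan states no sample size, power, SD or numeric d, so there is no figure of its own to reproduce. What follows is illustration under stated assumptions.

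**Inputs (all assumed)**
- n per arm: 20 to 100. The Design section says only that the trial is small.
- Allocation: 1:1. The ratio is not stated.
- *Small*: d = 0.2. The SAP gives no number.
- r, the pretest-posttest correlation: 0.3 to 0.8. Not stated.

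**Formulas**
- Residual-SD scale: SE(d) = √(2/n).
- Raw-SD scale: SE(d) = √(2(1−r²)/n).
- 95% interval: d ± 1.96·SE. The smallest observed d whose interval excludes zero is therefore 1.96·SE.
- n per arm at which 1.96·SE equals d: 2(1−r²)(1.96/d)², with the factor (1−r²) dropped for the residual SD.
- Chance under no effect that one outcome reaches c in the favourable direction: 1 − Φ(c/SE).

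**1. Interval half-width (also the smallest d that excludes zero)**

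| Standardiser | n = 20 | 30 | 50 | 100 |
|---|---|---|---|---|
| Residual SD | 0.62 | 0.51 | 0.39 | 0.28 |
| Raw SD, r = 0.3 | 0.59 | 0.48 | 0.37 | 0.26 |
| Raw SD, r = 0.6 | 0.50 | 0.40 | 0.31 | 0.22 |
| Raw SD, r = 0.8 | 0.37 | 0.30 | 0.24 | 0.17 |

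For example, at 20 per arm on the residual SD, SE = √(2/20) = 0.316 and 1.96 × 0.316 = 0.62, so d = 0.2 has the interval −0.42 to 0.82. At 50 it is −0.19 to 0.59, and at 100 it is −0.08 to 0.48. The most favourable cell is 100 per arm, raw SD, r = 0.8, where the interval is 0.03 to 0.37.

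**2. Size needed to exclude zero**

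For an observed d of 0.2, 2(1.96/0.2)² = 192.1 per arm on the residual SD. Multiplying by (1−r²) gives 174.8, 122.9, 98.0 and 69.1 on the raw SD at r = 0.3, 0.6, 0.7 and 0.8.

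For an observed d of 0.5 the values are 30.7 (residual), then 28.0, 19.7 and 11.1 (raw, r = 0.3, 0.6 and 0.8). An observed d of 0.8 already excludes zero at 20 per arm: 0.8 ± 0.62 is 0.18 to 1.42.

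**3. Chance that one given outcome reaches d ≥ 0.2 with no true effect**

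| Standardiser | n = 20 | 30 | 50 | 100 |
|---|---|---|---|---|
| Residual SD | 26.4% | 21.9% | 15.9% | 7.9% |
| Raw SD, r = 0.3 | 25.4% | 20.8% | 14.7% | 6.9% |
| Raw SD, r = 0.6 | 21.5% | 16.6% | 10.6% | 3.9% |
| Raw SD, r = 0.8 | 14.6% | 9.8% | 4.8% | 0.9% |

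For d ≥ 0.5 on the residual SD the chances are only 5.7%, 2.6%, 0.6% and below 0.1%. The problem is concentrated at the small end.

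Simulation of 40,000 null ANCOVAs per cell, with equal pretest and posttest variance, agrees. At r = 0.6 the residual SD gives 26.7/22.1/16.1/8.2%, the pooled pretest SD 21.9/16.9/10.9/4.0%, and the pooled posttest SD 21.9/16.9/10.8/4.0%.

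**4. Effect of the SD choice**

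Residual-scale d equals raw-scale d times 1/√(1−r²), which is 1.05, 1.25 and 1.67 at r = 0.3, 0.6 and 0.8. A raw d between 0.2·√(1−r²) and 0.20 changes label. The lower ends of that band are 0.19, 0.16 and 0.12. At 20 per arm the choice moves the chance in step 3 by 1.0, 4.9 and 11.8 percentage points.

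**The case against.** The strongest reply is that the plan is candid. It admits the lack of power, emphasises d without making it the sole result, sets no pass/fail rule, and collects usage and satisfaction data as well. The planned models yield standard errors, and silence in a half-page SAP does not forbid intervals. Asking whether an interval excludes zero also brings back the significance test that the sponsor chose to set aside. These points limit the harm: no estimate is biased, and intervals may well be produced. But nothing says they will be reported or used, and the one interpretive rule that is written down refers to the size of d alone. An interval also shows the range of compatible effects without requiring a significance verdict.

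The figures rest wholly on assumptions, and the result is not uniform across them. That stands: the chance in step 3 runs from 26% to 1%, and the most favourable cell excludes zero. Using 1.96 instead of a t critical value is slightly generous to the plan. With t on 2n−3 degrees of freedom, 0.62 becomes 0.64 at 20 per arm, and the required n rises by one or two.

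It can also be said that the remedy reaches large effects, which need no correction, and leaves *small* undefined. The proposed wording bars only a point estimate standing alone, so a large d can still be cited with its interval. Once the label carries no evidential weight, it needs no cut-off. The SD point would be a missing detail if it stood by itself, and it is treated as secondary here.

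**Conclusion.** The concern holds and should be fixed. The omissions are plain from the text: the plan gives evidential weight to a d at or above *small*, states no precision for it, and does not name its SD. This is a fault of interpretation; the models and estimates are not biased.

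The practical size depends on figures that the documents do not give. Over 20 to 100 per arm, an observed d of 0.2 has an interval that includes zero at every size on the residual SD, and on the raw SD unless the correlation is high and the arms are near the top of that range (about 98 per arm at r = 0.7, about 69 at r = 0.8). Observed effects of 0.5 or more are much less exposed. The choice of SD changes the label only for estimates just below the cut-off.

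**What to change.** Replace the last sentence of Main Analyses with:

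> For each outcome, the adjusted mean difference and Cohen's d (the adjusted difference divided by one pre-named raw SD, for example the pooled pretest or posttest SD, the same for all outcomes) will be reported with 95% confidence intervals, signed so that positive values mean benefit. Effect sizes will be interpreted as preliminary estimates in light of their intervals, across all outcomes; a small or larger point estimate alone will not be described as evidence of feasibility.

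The sponsor chooses the raw SD in advance. With equal pretest and posttest spread the two options perform alike, as the simulation shows. A narrow pretest spread is possible, though the documents give no data on it: youth must "NOT currently be in or have previously participated in a clinical trial", and of the knowledge scale the plan says "This measure has been created for the purposes of this study". A narrow pretest spread would enlarge a d scaled by the pretest SD.

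The cost is one SAP sentence and a few table columns, with no new data and no change to the models. The sponsor gives up some freedom in its claims and must commit to one SD. The usage and satisfaction data keep their place as separate information on feasibility.
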